#### **DAISY DRAIN Removal:**

The user who has undergone IFU training will remove the *DAISY* drain after at least two hours post CD based on clinical management. Suction will be discontinued, and the participant observed for 30 minutes before removal. One method of determining if the *DAISY* drain is no longer needed is by checking and documenting uterine tone. If uterine tone has returned to normal as assessed by palpation, the *DAISY* drain may be removed. (Note: If the uterine tone has not returned to normal, the user may choose to leave the drain in place and resume suction.) Upon drain removal, suction is briefly reapplied to collect any blood in the lumen after the 30-minute resting period. **Suction must be discontinued before the drain is removed.** Placing one hand on the abdomen to support the uterus while the other hand slowly withdraws the drain, the person removing the drain will evaluate the ease of drain removal. [See “Instructions for Use” provided to the user.]

## **6.0 STUDY DESIGN AND METHODOLOGY**

This is a prospective, single-arm, device evaluation study of five (5) obstetrical surgeons placing the drain with low-level suction in ten (10) women undergoing elective, non-emergent cesarean delivery.

### **TEST ENVIRONMENT**

The intended test environment is the operating room where the intended users (Obstetrical-Surgeons) are performing a CD. This is a single-center study to be conducted under the approval of the Institutional Review Board associated with the center. Each use of the *DAISY* drain will be documented via user questionnaire and participant case report form (CRF). As this is a device

evaluation study, the study focuses more on the users and less on the participant. However, some participant data will be necessary to collect to comply with the IFU. Further, we intend to assess participants during the post operative visit to ensure that any longer-term adverse effects are detected.

## **NUMBER OF USERS & PARTIPANTS**

In this study, 5 (five) users will place the *DAISY* drain in ten (10) participants do not have any of the contraindications for drain use at the time of the CD. Each user will place the drain at least once but no more than three times. After each obstetrical surgeon uses the *DAISY* drain, they will be asked to complete a questionnaire (Appendix 1).

The *DAISY* drain and Instructions for Use (IFU) will be evaluated qualitatively for the following including:

- ease of drain placement by obstetrician-surgeon
- appropriate size of drain
- appropriate final location of the deployed drain and incidence of improper placement
- ease of drain connection to suction tubing
- ease of drain removal
- perceived effectiveness of suction
- clarity of the IFU

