### 3.0 OBJECTIVES

This is a device evaluation study in 10 women who are undergoing a planned CD or non-emergent CD. Obstetrical-surgeon use of the technology in the operating room provides the Sponsor with the important information on how the intended user population interacts with the drain, ease of placement, and effects of adding suction during a clinical case. Further, the Sponsor wants to test the accuracy of the Instructions for Use document.

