### *Consenting:*

The Principal Investigator or research team member may consult a list of eligible patients based on predicted delivery dates. A list of participants who meet/ did not meet eligibility criteria will be maintained in a screening log by the study team. This log will contain identifiable information and is maintained by the team for determining eligibility and data collection purposes. The log also helps the study team to ensure that a participant who declined participation is not approached again upon admission to labor and delivery. IRB approval will be obtained prior to entering data in the screening and enrollment logs. The enrollment log will be a separate log that will contain the key linking participant information with the Participant ID. Each ID will be assigned to participants in a sequential order (e.g., 01-001, 01-002, 01-003....). Participant initials will not be included in the ID. Logs will be stored on password-protected desktops of the study team in a research folder accessible to the study team only. The participant IDs will be used on case report form (CRF) pages and the drain use questionnaire.

The team member will approach potentially eligible patients either in the office or clinic during the pre-operative visit. Patients who initially meet the enrollment criteria will be offered study

participation after a thorough presentation by the study PI, sub-investigator, or research coordinator at the pre-operative visit. At that time, all study risks will be discussed, and the consent form is signed should the patient choose to participate. Some participants may choose to take the consent materials home and return them later.

An updated list of consented participants will be available to the study team along with their participant numbers on a weekly basis. It is expected that at least twice as many participants will be consented as those that meet all inclusion/exclusion criteria at the time of the CD. Enrollment is considered “complete” when all inclusion and exclusion (contraindications) have been fully met

*Drain Placement:*

Described in Section 5

*Drain Removal:*

Described in Section 5

*Data Collection:*

User feedback is collected on a standardized form [see Appendix 1]. Limited participant data will be collected for the purposes of screening and device evaluation. [see Appendix 2] Sonographic images of drain placement may be recorded, printed, and placed in the participant’s study file.

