## NON-SIGNIFICANT RISK DETERMINATION

A significant-risk (SR) device study is defined by the United States Food and Drug Administration (<https://www.fda.gov/media/75459/download>) as one that:

- Is intended as an implant *and* presents a potential for serious risk to the health, safety, or welfare of a subject;
- Is purported or represented to be for use supporting or sustaining human life and presents a potential for serious risk to the health, safety, or welfare of a subject;
- Is for a use of substantial importance in diagnosing, curing, mitigating, or treating disease, or otherwise preventing impairment of human health and presents a potential for serious risk to the health, safety, or welfare of a subject;
- or otherwise presents a potential for serious risk to the health, safety, or welfare of a subject.

A Non-Significant Risk (NSR) device study is one that does not meet the definition for an SR device study. This study poses no significant risks, does not meet the definition above, and tests a device that is considered exempt from FDA clearance. The only “off label” use of the drain is the addition of low-level suction. The Sponsor has identified the following risks and mitigations to further explain the justification for the NSR determination:

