**APPENDIX 1**  
**DEVICE USE QUESTIONNAIRE**

Surgeon Name: \_\_\_\_\_

Obstetrician

Fellow

Resident (Circle one)

Years of experience in Obstetrical Surgery: \_\_\_\_\_

Date of Evaluation: \_\_\_\_\_ Placement #: 1 2 3 (Circle One)

Type of Suction Tube used (Brand & ID): \_\_\_\_\_

This Questionnaire aims to evaluate a set of aspects related to the use of the Daisy® device by the personnel in attendance. You are asked to indicate your level of agreement for each of the questions posed below, according to the scale of responses, place a check mark in the appropriate box.

	Strongly Agree	Agree	Neutral	Disagree	Strongly Disagree
Device training clearly explained insertion, use and removal of the device.					
The Instructions for Use (IFU) are clear and concise.					
The Daisy was easy to insert through the cervix.					
The Daisy was easy to properly position within the uterus.					
The Daisy was easily visualized in the lower uterine segment at time of placement.					
The Tube of the Daisy was easily advanced through the vaginal canal.					
The Cap of the Daisy was easily identified & retrieved outside the introitus.					
The Cap of the Daisy was easy to remove from the Tube.					
The Cap of the Daisy had adequate retention in the Tube.					
The Daisy did not interfere with the closure of the hysterotomy incision.					
The Daisy Tube fits easily into standard suction tubing.					

The suction tubing was easy to secure to the leg of the participant using the provided adhesive Catheter Anchors.					
The Daisy remained in place until elective removal.					
The estimated blood loss from the uterus was easy to determine.					
Use of the Daisy did not interfere with routine OR or PACU practices.					
The force to remove the Daisy was acceptable.					
Overall, the Daisy was easy to use.					
The Daisy drained without intervention (clot removal). Describe any clots or interventions in the Comments below.					
Blood flow was easy to visualize through the Tube.					
Overall, the Daisy met all the user needs as intended.					

Other comments regarding the use of the Daisy: \_\_\_\_\_

\_\_\_\_\_

\_\_\_\_\_

\_\_\_\_\_

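### Two of the seven stated evaluation aspects, perceived effectiveness of suction and drain size, have no prompted item on the user questionnaire

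*Protocol*

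**What the plan says.** Section 6.0, under Number of Users & Participants, says that the drain and its instructions will be evaluated qualitatively and gives seven bullets. The second is "appropriate size of drain" and the sixth is "perceived effectiveness of suction". The same section names the instrument: "After each obstetrical surgeon uses the *DAISY* drain, they will be asked to complete a questionnaire (Appendix 1"). The Data Collection paragraph under Methods repeats it: "User feedback is collected on a standardized form [see Appendix 1"].

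Suction is prominent elsewhere. Section 3.0 lists "effects of adding suction during a clinical case" among the things that surgeon use should tell the sponsor. The Non-Significant Risk Determination in Section 7.0 says that the only off-label "use of the drain is the addition of low-level suction".

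Appendix 1 has 20 statements, each rated from strong agreement to strong disagreement, followed by an open comment line. Two statements name suction: "The Daisy Tube fits easily into standard suction tubing" and "The suction tubing was easy to secure to the leg of the participant using the provided adhesive Catheter Anchors". Section 8.0 scores the ratings 1 to 5, summarises them mainly by means, medians and standard deviations, and commits the sponsor to follow up every response in the two disagreement categories.

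**The concern.** The Test Environment paragraph of Section 6.0 says that the study is more about the users than the participants. Its main product is therefore what the surgeons report, and the form decides what they are asked. If the form has no question on a stated aspect, no later analysis can supply the answers.

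The gap matters most for suction, which by the protocol's own account is the one off-label element. Surgeons are in a position to judge it: Section 5.0 says that efficacy can be seen directly from contraction of the uterus once the incision is repaired. There are only ten placements by five surgeons, and each one completed on the present form loses a rating that later recall would replace poorly.

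**Working it through.** The protocol gives no sample-size or power figure on this point, so there is nothing to reproduce. The check is a mapping of the seven bullets in Section 6.0 to the 20 statements in Appendix 1, followed by a search for other sources of user opinion.

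| Aspect in Section 6.0 | Direct items in Appendix 1 | Indirect or other sources |
|---|---|---|
| 1. Ease of placement | Yes: passing the cervix, positioning, visualisation, advancing the tube, handling the cap | – |
| 2. Size of drain | None | Ease of insertion, no interference with closure, removal force, tubing fit |
| 3. Final location, improper placement | Yes: positioning, staying in place | Appendix 2 ultrasound of device position |
| 4. Connection to tubing | Yes: tubing fit | – |
| 5. Ease of removal | Yes: removal force | – |
| 6. Perceived effectiveness of suction | None | Drainage without clot removal, visible blood flow, ease of estimating blood loss |
| 7. Clarity of the instructions | Yes: clarity of the instructions | Training item |

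Five aspects have at least one direct item and two have none.

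With one form per placement, the study yields at most 10 × 20 = 200 scored responses. On suction effectiveness it yields 10 × 0 = 0, and on drain size 10 × 0 = 0.

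Other possible sources:

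- **The general items.** The overall ease-of-use and user-needs statements name neither topic, so a low score could not be traced to either.
- **The comment line.** It is unprompted and unscored, so silence cannot be read as approval.
- **Feedback to company observers** (User Training, Section 6.0). Its stated purpose is to check that the instructions are clear and informative.
- **Follow-up of disagreement** (Section 8.0). It is triggered by scored items, so neither topic can trigger it directly.
- **Appendix 2.** It records suction level, tone, the ultrasound scale and other ultrasound findings at three time points, total estimated blood loss and uterotonic use. Under Section 5.0 the three assessments come at the end of two hours, five minutes after suction is reduced, and 30 minutes after that. All three follow the start of suction and come in a fixed order, so a change in suction level cannot be separated from elapsed time. With a single arm (Section 6.0), suction also cannot be separated from uterotonics.

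A rating of suction would not need a new time of completion. The form already asks about staying in place and removal force, which are known only at the end of device use.

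**The case against.** The strongest reply is that Section 6.0 promises a qualitative evaluation and does not say that each bullet must be a scored item or must come from Appendix 1 alone. Each use is documented by questionnaire and case report form together, and participant data are collected partly for device evaluation. Tone is assessed by palpation, which is itself a clinician's judgement. A badly sized drain would probably lower the ratings for insertion, closure or removal, and any disagreement there would be followed up.

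Much of this stands. A reader might infer that users have no means of expressing a view on these two aspects. The documents do not support that, because the comment line and the indirect items exist. A reader might also infer that the Section 3.0 objective on suction must fail. That does not follow either: the objective speaks of effects, and Appendix 2 describes the uterine response.

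What does not stand is that these sources meet the sixth bullet as written. It asks for perceived effectiveness. A palpated tone is a finding about the uterus, not an opinion on whether suction worked, and Section 5.0 assigns the later assessments to the investigator, who may not be the surgeon who placed the drain. For size, the indirect items record possible consequences of a poor fit without asking about the cause.

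**Conclusion.** The point holds as a moderate mismatch between instrument and aims. Two of seven listed aspects have no prompted or scored user item, and one of them concerns the only off-label feature. The proportion should not be read as a measure of lost information, since the bullets are not ranked and the list is introduced as not exhaustive.

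A reader might treat this as an error that invalidates the study. The documents do not support that: this is a descriptive, single-arm evaluation in ten participants, the protocol states no hypothesis test, and no stated estimate becomes biased. Nor is it a matter for a separate analysis plan, because the form is fixed in the protocol's own appendix.

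The conclusion assumes that Appendix 1 is used as printed, once per placement, and that no other user form exists. The protocol names none.

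**What to change.** Before first use, add three statements to Appendix 1 on the existing five-point scale:

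- suction was effective in evacuating blood from the uterus;
- suction was effective in maintaining uterine tone;
- the drain was of an appropriate size for this participant.

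Keep the two suction statements separate, since a surgeon may agree with one and not the other. The Section 8.0 summaries and the follow-up of disagreement then apply to them without further change, and ten placements give up to 10 × 3 = 30 additional ratings. In Section 6.0, state beside each bullet which Appendix 1 item answers it, and name the Appendix 2 fields that supplement the suction items. The report should present the new ratings as users' perception, not as evidence that suction caused the uterine response.

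The cost is a short amendment and slightly more form-filling per case. Appendix 1 is part of the protocol, and item d) of the Principal Investigator Responsibilities requires amendments to be submitted to the IRB and approval awaited, so notification alone would not do. No device use or clinical procedure changes. If placements have already been made on the present form, the new items cover only the remaining ones, and the report should give that denominator.

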## **METHODS**

### *User Training:*

Minimal product training is necessary other than a review of the IFU. Company personnel will initially observe the insertion and removal procedures and secure feedback post placement and removal to be sure that the IFU is clear and appropriately informative.

### *Consenting:*

The Principal Investigator or research team member may consult a list of eligible patients based on predicted delivery dates. A list of participants who meet/ did not meet eligibility criteria will be maintained in a screening log by the study team. This log will contain identifiable information and is maintained by the team for determining eligibility and data collection purposes. The log also helps the study team to ensure that a participant who declined participation is not approached again upon admission to labor and delivery. IRB approval will be obtained prior to entering data in the screening and enrollment logs. The enrollment log will be a separate log that will contain the key linking participant information with the Participant ID. Each ID will be assigned to participants in a sequential order (e.g., 01-001, 01-002, 01-003....). Participant initials will not be included in the ID. Logs will be stored on password-protected desktops of the study team in a research folder accessible to the study team only. The participant IDs will be used on case report form (CRF) pages and the drain use questionnaire.

The team member will approach potentially eligible patients either in the office or clinic during the pre-operative visit. Patients who initially meet the enrollment criteria will be offered study

participation after a thorough presentation by the study PI, sub-investigator, or research coordinator at the pre-operative visit. At that time, all study risks will be discussed, and the consent form is signed should the patient choose to participate. Some participants may choose to take the consent materials home and return them later.

An updated list of consented participants will be available to the study team along with their participant numbers on a weekly basis. It is expected that at least twice as many participants will be consented as those that meet all inclusion/exclusion criteria at the time of the CD. Enrollment is considered “complete” when all inclusion and exclusion (contraindications) have been fully met

*Drain Placement:*

Described in Section 5

*Drain Removal:*

Described in Section 5

*Data Collection:*

User feedback is collected on a standardized form [see Appendix 1]. Limited participant data will be collected for the purposes of screening and device evaluation. [see Appendix 2] Sonographic images of drain placement may be recorded, printed, and placed in the participant’s study file.

**VISIT SCHEDULE**

Visit	Visit 1	Visit 2	Visit 3
Procedures	Patient education and consent	Final Enrollment and Drain placement.	Post-partum visit
Timing	Pre-surgical	Drain Placement during CD/ Removal in Recovery Room	4-8 weeks post-partum
Evaluations	Screening using Medical History and current prenatal status	User evaluations Uterine tone assessments Ultrasounds Adverse events	Adverse events
Stipend	No	Yes	Yes

*Participant Stipend:*

Participants will be compensated at a rate of \$100 upon completion of Visit 2 and an additional \$50 for the completion of Visit 3 for a total of \$150.

*Duration of Participation:*

Participants will be considered initially enrolled at the time of consent which may occur a week or more prior to the CD. Participants are expected to be followed for up to the post-partum visit.

## **ALTERNATIVES TO PARTICIPATION**

Participants will receive the standard care per clinical indication regardless of participation in the study. Declining to participate will not affect clinical care.

## **WITHDRAWAL OF PARTICIPANTS**

Participants will be withdrawn from the study if, after obtaining informed consent, the participant no longer meets the inclusion/exclusion criteria. If participants self-withdraw from the study, any data abstracted up until that point may be used in data analysis of participant characteristics. No further measurements or data will be collected after participant withdrawal or study completion.

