## 1.0 SUMMARY

The goal of this study is to obtain user feedback while placing and observing the *DAISY* uterine drain with wall suction. This study defines the obstetrical surgeons as “users” and the patients in whom the drain is placed as “participants.” Participants are pregnant women who are undergoing cesarean delivery (CD), who have not entered active labor, who have consented to drain placement and who have met all the inclusion/exclusion criteria. Users are staff or fellow obstetrical surgeons who will use the drain and provide the evaluation.

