### 4.0 STUDY POPULATION

As described above, this study defines the obstetrical surgeons as “users” and the patients in whom the drain is placed as “participants.” The participants consist of women undergoing planned CD for reasons unrelated to this study. We expect to enroll five (5) obstetrical surgeons of various levels of experience who will each place a drain in one to three participants for a total of 10 participants who are qualified based on the Instructions for Use (IFU) *and* who consent to participation. The following contraindications serve as exclusion criteria.

- Known intrauterine or cervical pathology that would interfere with device placement and/or use
- Ongoing intrauterine pregnancy
- Untreated uterine rupture
- Unresolved uterine inversion
- Current cervical cancer
- Current purulent infection of vagina, cervix, or uterus
- Retained products of conception
- Arterial bleeding requiring surgical or angiographic embolization
- Indication for hysterectomy
- Lack of study consent.

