The hysterotomy is then closed taking care not to loop any sutures around the drain. Blood flow through the lumen will be measured by attaching the suction tubing to a fluid collection container (e.g., bag, or calibrated suction canister). Tubing must be secured to the thighs using a foley catheter securing adhesive to avoid displacement before attaching to the suction canister. For this Protocol, 100mmHg of suction is recommended to induce uterine involution. The *DAISY* drain will remain in place for a minimum of 3 hours while the Participant is in the recovery unit. At the end of 2-hours, the uterus will be evaluated by manual palpation and abdominal ultrasound. The abdominal ultrasound will be performed to document device placement and to assess uterine involution, approximate uterine size and uterine cavity size, presence of intrauterine clots or retained products of conception. Following the ultrasound, the suction is to be reduced to 10mmHg for 5 minutes. After 5 minutes, the investigator will again assess uterine tone and perform another ultrasound. After the second ultrasound, the Daisy is left in place with the suction at 10mmHg for 30 minutes. After 30 minutes, the investigator is to again assess uterine tone manually and perform the third ultrasound.

NOTE: If the uterine cavity is assessed by ultrasound and/or clinically determined to contain clots or products of conception, the device will be removed after discontinuation of suction, the study participant discontinued, and management undertaken per institutional protocol. Thirty minutes before device removal, any suction applied must be discontinued to observe for any additional bleeding. Clinical management of the subject will determine the time for device removal, but the device must be removed within 24 hours of placement. [See “Instructions for Use” provided to the user.]

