## RISK & RISK MITIGATION

The following risks have been identified as “potential” based on similar devices:

- Perforation: The risk of perforation is mitigated by the placement of this drain under direct observation followed by an ultrasound confirming correct placement after closure. In addition, the drain is constructed of smooth, atraumatic materials.
- Endometritis: Endometritis is mitigated by selection of appropriate materials, selection of appropriate participants, and limited drain dwelling time. Endometritis can occur regardless of device use. To evaluate the occurrence of endometritis, participants will be followed out to the time of the post-partum visit.
- Vaginitis or tissue trauma: Vaginitis or tissue trauma is mitigated by using non-irritating materials and an atraumatic drain design. To evaluate for the occurrence of vaginitis or tissue trauma, participants will be followed out to the time of the post-partum visit.
- Infection: Infection is mitigated through the direction of drain placement, sterility of the drain, and limited time of exposure to the drain (~2.5 hours) in addition to careful participant selection.
- Loss of Participant Confidentiality: The principal risk of a signed consent document would be the potential harm resulting from a breach of confidentiality. Every precaution will be taken to minimize this. The original signed consent documents will be stored in the research office which will be locked when not attended. Electronic logs will be stored in password protected desktop computers, accessible only to the research team. Data will

be stored according to institutional policy. At any given time, there will be 1 to 3 people from the Sponsor and/or site's research team present to abstract data. De-identified data will be collected in the database which will be accessible to outside institution team members. Data transferred out of the site will be de-identified data with the study ID number. The key containing the study ID number with the participant information will be accessible to the study team only and will be stored securely on password-protected computers. No genetic information will be collected for this study.

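### Withdrawal and discontinuation rules, as written, can end safety follow-up for women already treated with the drain, contradicting the promised follow-up to the post-partum visit

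*Protocol*

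**What the plan says.** Two rules can remove a participant.

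- **Withdrawal of Participants (Section 6.0).** The trigger is: "Participants will be withdrawn from the study if, after obtaining informed consent, the participant no longer meets the inclusion/exclusion criteria". The consequence is: "No further measurements or data will be collected after participant withdrawal or study completion". The one sentence on using data gathered before withdrawal concerns women who withdraw themselves; for them, "any data abstracted up until that point may be used in data analysis of participant characteristics".
- **NOTE in Section 5.0.** If clots or products of conception are found in the cavity after placement, "the device will be removed after discontinuation of suction, the study participant discontinued, and management undertaken per institutional protocol".

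The eligibility list in Section 4.0 includes conditions that can arise or come to light after placement, among them "Retained products of conception" and "Arterial bleeding requiring surgical or angiographic embolization". An indication for hysterectomy and a current purulent infection of the vagina, cervix or uterus are also listed.

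Against this stand the safety commitments. Test Environment says participants will be assessed at a post-operative visit so that longer-term adverse effects are found. Visit Schedule and Adverse Event Reporting place adverse event collection at Visits 2 and 3, with Visit 3 at 4 to 8 weeks. Risk & Risk Mitigation says: "To evaluate the occurrence of endometritis, participants will be followed out to the time of the post-partum visit". It makes the same promise for vaginitis and tissue trauma. The Non-Significant Risk Determination presents these mitigations as part of its justification.

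**The concern.** A rule about eligibility is written so that it also reaches women who have already been treated, and it switches off data collection when it applies. The conditions that trigger it after placement are not a random subset. Bleeding, retained tissue, clots and infection mark the women whose later course matters most for judging the drain under suction. If the site follows the text, those women have no Visit 3 adverse event check, while women with an uneventful course do. Late safety would then be described mainly in the women least likely to show a problem, and a mitigation offered in the risk determination would not operate where it is most needed.

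**Working it through.** There is no figure in the protocol to reproduce: the number of participants (10) is given without a derivation, and no participant-level rate is planned. The check is therefore mainly a comparison of texts.

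**Step 1. Does either rule stop at placement?** The withdrawal trigger starts at consent and has no end point. The Section 5.0 NOTE applies only after placement, because it follows the ultrasound assessments made with the drain in place.

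**Step 2. Does either rule exempt safety data?** No. The sentence ending data collection has no exception. The NOTE lists removing the device and discontinuing the participant as separate acts, does not define the second, and does not mention Visit 3.

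**Step 3. What is lost, read literally?** Section 5.0 and Appendix 2 plan three assessments of tone and ultrasound.

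| Clots or products found at | Planned assessments lost | Visit 3 adverse event check |
|---|---|---|
| First assessment | 2 of 3 | lost |
| Second assessment | 1 of 3 | lost |
| Third assessment | 0 of 3 | lost |

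Stopping the device assessments may follow from clinical management and is not questioned here. The contradiction lies in the last column.

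**Step 4. What is kept?** The triggering finding is made before withdrawal takes effect. It can be recorded through the Visit 2 adverse events and ultrasounds, the 24-hour report to the IRB if it is a device-associated serious event, and the questionnaire completed after each use.

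**Step 5. Do the kept data enter the summaries?** Unclear. The only sentence on this covers self-withdrawal and limits use to participant characteristics. Nothing is said for withdrawal by the study.

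**Step 6. Scale.** One woman among 10 is 1/10 = 10% of the safety data. If k women have no Visit 3 data and no late event is seen in the other 10 − k, the true count of late events among the 10 lies anywhere from 0 to k:

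| k without Visit 3 | Observed | Exact 95% upper limit | Possible proportion among all 10 |
|---|---|---|---|
| 0 | 0/10 | 30.8% | 0% |
| 1 | 0/9 | 33.6% | 0% to 10% |
| 2 | 0/8 | 36.9% | 0% to 20% |
| 3 | 0/7 | 41.0% | 0% to 30% |

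Upper limits are two-sided Clopper-Pearson, 1 − 0.025^(1/(10 − k)). The loss of precision is small. The concern is which women are missing.

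**Step 7. How likely is at least one case?** The protocol gives no rate, so a range is assumed. With P = 1 − (1 − p)^10:

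- p = 2%: 1 − 0.98^10 = 18%
- p = 5%: 1 − 0.95^10 = 40%
- p = 10%: 1 − 0.90^10 = 65%
- p = 20%: 1 − 0.80^10 = 89%

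**The case against.** The best defence is that the eligibility rule was meant for women lost between consent and surgery. Section 4.0 lists contraindications. Number of Users & Participants applies them at the time of the cesarean. Consenting expects at least twice as many women to consent as will qualify then. Visit Schedule puts final enrollment at Visit 2. Treating a later purulent infection as a withdrawal trigger would also let a complication end the follow-up meant to detect such complications, which can hardly be intended. This is persuasive about intent, but the wording does not carry it, and it does not touch the Section 5.0 NOTE, which is expressly about women already treated. It remains true that the NOTE says discontinued rather than withdrawn, so its link to the ban on further data is itself a reading. The protocol does not settle the matter either way.

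Three stronger readings are tempting and are not supported:

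- *A reader might infer that device failures and harms vanish from the results.* The rule stops only further data, and the triggering event has the routes onto the record set out above. A contrast such as 1/10 (10%, exact 95% interval 0.3% to 44.5%) turning into 0/9 is correct arithmetic, but it illustrates an exclusion from the denominator that the protocol never states.
- *A reader might infer that failed insertions are not counted,* because Section 1.0 describes participants as "the patients in whom the drain is placed as" participants. That phrase separates patients from surgeons. Elsewhere consented women are already called participants, improper placement is to be evaluated, and Appendix 1 rates insertion and positioning.
- *A reader might want every such event classed as a device failure, with no replacement allowed.* The protocol defines no device-failure endpoint, and retained products need not be due to the drain.

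It is also fair that this is a 10-woman user evaluation whose stated analysis is mainly means, medians and standard deviations of questionnaire scores, and that analysis sets are commonly left to a statistical analysis plan. That lowers the weight of the point. It does not remove a contradiction between a stated data-collection rule and a stated safety commitment.

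**Conclusion.** The point holds as an internal contradiction: the protocol is wrong as written. The withdrawal rule and the Section 5.0 NOTE, followed literally, can cancel the Visit 3 adverse event check for women already exposed to the drain under suction, while other sections depend on that check to find endometritis, vaginitis, tissue trauma and other longer-term harm. What is at risk is the later course of the triggering event and any late event, not the triggering event itself. Whether data gathered before withdrawal by the study enter the summaries is left open.

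Each affected woman is 10% of the safety data. How many there would be is unknown; the rates used above are assumptions. For exclusions arising after placement, the conclusion rests on taking the eligibility rule at its word. For clots or products of conception, it rests on reading discontinued as leaving the study. The point should be corrected, but because the study centers on user feedback and the event is likely to be recorded, it falls short of a must-fix.

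**What to change.** 1. In Withdrawal of Participants, limit withdrawal for eligibility to the time before drain placement is attempted.
2. In Withdrawal of Participants and the Section 5.0 NOTE, separate stopping device use from leaving the study. After device use stops, adverse event collection continues through Visit 3 unless the participant withdraws consent.
3. State that data from every participant with an attempted placement stay in the user and safety summaries.

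The NOTE, Withdrawal of Participants, Adverse Event Reporting and Risk & Risk Mitigation should then be reconciled. No rule on clinical management is proposed; when the device is removed and how the woman is treated are outside this point.

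The cost is a change of protocol wording, submitted to the IRB as an amendment. No visit is added, since Visit 3 is already scheduled for participants.
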